6.3 Drugs

Esomeprazole, 20mg/tablet, AstraZeneca AB, Sodertalje, Sweden.

Bismuth potassium citrate, 300mg/capsule (110mg elemental bismuth), Dawnrays Pharmaceutical Limited, Suzhou, Jiangsu, China.

Amoxicillin, 250mg/capsule, Ruiyang Pharmaceutical Co. Ltd., Shandong, China.

Clarithromycin, 250mg/tablet, Shanghai Abbott Laboratories Co. Ltd., Shanghai, China.

Metronidazole, 200mg/tablet, Shanghai Xinyi Wanxiang Pharmaceutical Industry Company Limited, Shanghai, China.

Levofloxacin, 500mg/tablet, Daiichi Sankyo Pharmaceutical Beijing Co., Ltd., Beijing, China.

7. *H. pylori* Culture and Antibiotic Susceptibility Testing

Tissue samples will be obtained from gastroscopic biopsy. The biopsy specimens will be cultured and maintained on brain heart infusion agar medium (OXOID, Basingstoke, UK) containing 5% defibrinated sheep blood under microaerophilic conditions (85% N₂, 10% CO₂, 5% O₂) at 37°C. All isolates will be stored in brain heart infusion broth (Difco Laboratory, Detroit, MI, USA) supplemented with 30% glycerol at -80°C. Clinical isolates will be also identified as *H. pylori* using positive tests for urease, oxidase, catalase and Gram staining.

Minimal inhibitory concentrations (MIC) of clarithromycin, metronidazole, and levofloxacin will be determined by the two-fold agar dilution method. *H. pylori* is suspended in saline and measured using a spectrophotometer. The bacterial suspensions (10⁸ colony forming units per milliliter) are then plated with an inoculator (Sakuma Seisaku, Tokyo, Japan) onto agar plates containing various concentrations of above antibiotics. After three days of microaerophilic incubation, MIC is defined as the lowest drug concentration that prevented visible growth of bacteria. ATCC43504 is used as the quality control. Clarithromycin >2 µg/mL, metronidazole >8 µg/mL, levofloxacin >2 µg/mL is defined as resistance breakpoints.

8. Safety evaluation

From the beginning of that patients signed the informed consent and are selected for trial to one month after the end of treatment, any adverse medical events, regardless of whether a causal relationship with the study medication, will be judged to be Adverse Event (AE).

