
Exclusion Criteria
	
 1. Previous H. pylori eradication therapy 2. Less than 18 years old 3. With history of H. pylori infection treatment 4. With previous gastric surgery 5. Major systemic diseases 6. Pregnancy or lactation 7. Allergy to any of the study drugs 8. Administration of antibiotics, bismuth, antisecretory drugs in 8 weeks prior to inclusion

Arms and Interventions
	
1. Empirical therapy
 
Esomeprazole 20 mg, bismuth potassium citrate 600 mg taken twice a day, amoxicillin 1 g, and metronidazole 500 mg taken three times a day for 14 days.
 
2. Tailored therapy
 
Tailored therapy is based on antimicrobial susceptibility of clarithromycin, metronidazole and levofloxacin. according to antibiotic resistance pattern included esomeprazole 20mg bid, amoxicillin 1g bid, with a third drug (clarithromycin 500mg bid, metronidazole 400mg bid, or levofloxacin 500mg qd) for susceptible strains, or with bismuth 220mg bid plus metronidazole 400mg qid for triple-resistant strains. Study treatment regimens were all given 14 days.

Schedule
	
1. Enrollment
 
Obtain written informed form

	
Check eligibility criteria
 
Collect baseline characteristics
 
Undergo upper endoscopy with gastric biopsy and rapid urease testing
 
Conduct bacterial culture and antibiotic susceptibility testing
 
2. Allocation
 
After the written informed consents would be obtained from eligible patients, the independent research assistant will open envelopes by randomization sequence and telephone study staff to give them each patient's treatment allocation. Eligible patients will be randomly allocated to receive either tailored therapy or empirical therapy in a 3:1 ratio.
 
3. treatment
 
Study treatment regimens were all given 14 days. During the treatment period, the subjects kept a diary to monitor compliance and symptoms.
 
4. Follow-up
 
After the end of treatment, adverse events and compliance was surveyed. Six weeks after completion of therapy, H. pylori eradication was assessed by ¹³C-urea breath testing.

Outcome Measures
	
Primary Outcome Measure:
 
1. Helicobacter pylori eradication rate
 
Six weeks after completion of therapy, H. pylori eradication success is defined as negative result from urea breath test (<4%)
 
Secondary Outcome Measure

Final Protocol

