	
1. Rate of adverse events2. Compliance rate 
Other Pre-specified Outcome Measures:
 
1. Medical cost per patient of tailored or empiric therapy2. Ratio of medical cost to H. pylori eradication rate of each therapy3. Ratio of incremental medical cost to incremental H. pylori eradication rate of tailored compared with empiric therapy
--	---

Protocol Schedule

Study Period	Enrollment	Allocation	Treatment	Follow-up	
Visit	1st	2nd		3rd	4th
Time point (day)	-14th	0	0-14	15th	56th
Eligibility screen	✓				
Baseline characteristics	✓				
Endoscopy with biopsy and RUT	✓				
H. pylori culture and susceptibility testing	✓				
Written informed content	✓				
Therapy Allocation		✓			
Treatment			✓		
Adverse events				✓	
compliance assessment				✓	
¹³C-urea breath test					✓
Medical cost					✓

1. Background

Helicobacter pylori (*H. pylori*) resistance to antibiotics was main challenge to previous efficacy antibiotic regimens such as standard triple therapy(1). The prevalence of antibiotic resistance have been markedly increasing with time in most parts of the world. Concordantly, the antimicrobial eradication rate of *H. pylori* has been declining globally.(2) In China, clarithromycin, metronidazole and levofloxacin resistance show similar trends, and resistance rates have now reached 21~52% for clarithromycin, 61~95% for metronidazole, 20~54% for levofloxacin, and 21~37% for both clarithromycin and metronidazole.(3–5) Standard triple therapy had not been suitable for first-line therapy in China because the pooled eradication rate had declined to 74.5% as a meta-analysis showed.(6)

As a general rule, therapy for an infectious disease starts with identification of potentially useful antimicrobials and is largely based on the results of susceptibility testing. Systematic reviews or meta-analysis had proved susceptibility-based therapy was superior to 7–10 day triple therapies as first-line treatment.(7–9) Therefore, there is a critical need to antimicrobial susceptibility testing (AST) for individualized analysis of antibiotic resistance prior to definitive treatment.(2)

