2.2 The secondary objective

- (1) To compare the safety and compliance of tailored therapy with empiric modified bismuth quadruple therapy;
- (2) To evaluate the impact of antibiotic resistance on eradication rates;
- (3) To evaluate the cost-effectiveness of susceptibility-based tailored therapy in treating naïve patients with *H. pylori* infection.

3. Follow Diagram

4. Study Design

This study is a prospective, superiority-designed, multi-center, open-label, randomized controlled trial conducted in five hospitals in Shanghai, China including Renji Hospital, Ruijin Hospital, Zhongshan Hospital, Shanghai general Hospital, and Shanghai Tenth People's Hospital.

5. Study population

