6.1 Randomization and blinding

Eligible patients will be randomly allocated to receive either susceptibility-based tailored therapy (tailored therapy) or empirical bismuth quadruple therapy (empirical therapy) in a 3:1 ratio. An independent statistician at Shanghai Jiao Tong University College of Basic Medical Sciences generates the computerized random number sequence and used a permuted block randomization with a block size of eight. All investigators is masked to the randomization sequence. Allocation is concealed in an opaque envelope until the intervention was assigned. Envelopes will be kept at Renji Hospital. After the written informed consents would be obtained from eligible patients, the independent research assistant will open envelopes by randomization sequence and telephone study staff to give them each patient's treatment allocation. This study is an open-labeled trial and patients are not blinded. The technicians, who perform the H. pylori tests (rapid urease test, culture, antimicrobial susceptibility testing, and urea breath test) or fill in the questionnaires, will be blinded to treatment allocation.

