8.2 Records and follow-up of AE

During the study, AE will be accurately recorded, including the time of occurrence, severity, duration, the measures taken and the outcome. Researchers will follow all the AE until the symptoms of patients disappeared or condition become stable. SAE should be tracked until a proper solution is found even though the study is over.

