8.3 Serious adverse event (SAE)

(1)The judgments of SAE:

- Death, Life-threatening,
- Leading to hospitalization or prolong hospitalization time,
- Permanent or severe disability,
- Congenital Anomaly/Birth Defect.

(2)SAE report system:

Principal investigator and the hospital ethics committee should be reported and SAE report form should be filled in within 24 hours by phone no matter whether any kinds of SAE are related with the drug in 30 days after the treatment. And the form should be reported to national drug administration in time by principal investigator. SAE should be promptly handled, closely tracked until it is properly solved.

Contact method:

1) Contact persons: [name] [name]

2) SFDA Safety Supervision

9. Outcome Measures

9.1 Primary Outcome Measure:

1. Helicobacter pylori eradication rate

Six weeks after completion of therapy, H. pylori eradication success is defined as negative result from urea breath test (<4%). If patients would be lost to follow-up urea breath testing, they will be scored as treatment failures in the ITT analysis. The eradication rate is defined as the number of patients who successful eradicate *H. pylori* divided by the total number of population for analysis.

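### Adverse events count until one month after treatment, but the last scheduled enquiry about them is on day 15

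*Combined protocol and SAP*

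**What the plan says.** All references are to the Final Protocol and Final SAP.

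- **Window.** Protocol Section 8 treats any untoward medical event, related to study drug or not, as an adverse event if it falls in this period: "From the beginning of that patients signed the informed consent and are selected for trial to one month after the end of treatment". Section 8.3 requires serious events to be reported "no matter whether any kinds of SAE are related with the drug in 30 days after the treatment".
- **Scheduled collection.** The Protocol Schedule ticks adverse events once, at visit 3 (day 15). The synopsis agrees: "After the end of treatment, adverse events and compliance was surveyed", followed at six weeks by the breath test alone. Visit 4 (day 56) is ticked for the breath test and medical cost.
- **Diary.** Protocol 9.2 and SAP 5.1 have patients keep a diary over the 14 treatment days. The same paragraph then defines the adverse-event rate as patients with any event over the analysis population, without stating a counting window.
- **General duty.** Protocol 8.2 says "During the study, AE will be accurately recorded, including the time of occurrence, severity, duration, the measures taken and the outcome", and that known events are followed until they resolve or stabilise.
- **Cost.** Protocol 9.3 includes the treatment of adverse events in each patient's medical cost.
- **Objective.** The first secondary objective in 2.2 is "To compare the safety and compliance of tailored therapy with empiric modified bismuth quadruple therapy".
- **Severity.** Protocol 8.1 and 9.2 each define mild, moderate and severe, in different terms.

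**The concern.** The window that the protocol sets for itself is wider than the period over which it arranges to ask. After day 15 no contact is planned at which a new non-serious event would be looked for. Whether such an event is recorded then depends on whether the patient reports it, whether site staff happen to learn of it, or whether its treatment cost comes to light. Safety is a named comparison between the arms, so late safety information would be gathered unevenly from patient to patient, and a reader of the report could not tell how complete it was.

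A smaller question follows. Because the rate definition gives no window, the documents do not say outright whether an event on, say, day 25 enters the numerator.

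**Working it through.** **Reproducing the plan's calendar.** Treatment ends on day 14. Six weeks later is 14 + 42 = day 56, which matches the schedule.

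**End of the Section 8 window.** With a month of 28, 30 or 31 days, the window closes on day 14 + 28 = 42, 14 + 30 = 44 or 14 + 31 = 45. The 30-day value matches 8.3 and is used below.

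**Days without a scheduled enquiry.** I assume that the day-15 survey looks back over everything up to and including day 15. The uncovered days are then 16 to 44: 44 - 16 + 1 = 29 days (27 or 30 for a month of 28 or 31 days).

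**As a share of the window.** The answer depends on the denominator:

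| Denominator | Days | Share uncovered |
|---|---|---|
| Consent (day -14) to day 44 | 59 | 29/59 = 49% |
| Day 0 to day 44 | 45 | 29/45 = 64% |
| Post-treatment part only, day 15 to day 44 | 30 | 29/30 = 97% |

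These are shares of calendar days, not of events or patients. The documents give no rate of late-onset events, so no count of missed events can be derived.

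**What a day-56 enquiry would involve.** Recall since the last survey would be 56 - 15 = 41 days. The visit falls 56 - 44 = 12 days after the window closes, so onset dates are needed to assign events to it.

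**How many patients it would reach.** Protocol 10.1 allows for 10% loss: 10% of 382 is about 38. The inflation actually applied is (286 - 260) + (96 - 87) = 26 + 9 = 35, or 35/382 = 9.2%. About 344 to 347 patients would be asked.

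**Severity wording, side by side.** In 8.1, mild and moderate events need no clinical treatment and severe events do. In 9.2, repeated in SAP 5.1, patients grade their own events by the effect on daily activities, with tolerability and discomfort mentioned in the lower grades, and treatment plays no part. An event that interferes considerably but needs no treatment is severe under 9.2 and does not meet the severe wording of 8.1. The SAP carries only the 9.2 scale.

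The Original Protocol has the same window, schedule and two scales, so the amendment did not create either mismatch.

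**The case against.** The best defence is that Section 8 says which events count and does not promise active questioning throughout. A reporting window wider than the solicited period is a legitimate design choice. Protocol 8.2 imposes a duty to record, 8.3 gives serious events a 30-day route, and the outcome that is analysed lines up well: a 14-day diary, a survey the day after treatment ends, and a rate defined in the diary paragraph. Much of this stands. The most natural reading of the rate is the 14-day diary rate, and on that reading nothing is lost from it. But 8.2 says what to record and how to follow known events, and 8.3 sets a reporting duty. Neither creates a contact at which a new event would be found.

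It is also fair that late events need not depend on patients volunteering them. Events that were treated may surface through the cost item at day 56, although the documents do not say how cost is gathered. The likeliest gap is late, non-serious, untreated events.

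A reader might infer from the 97% figure that nearly all safety data are uncollected. It does not show that: it leaves out the treatment period, when the diary runs, and any single survey at the end of treatment would give about the same value.

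A further objection concerns the remedy. Protocol 6.1 names in one sentence the technicians who do the breath test and those who "fill in the questionnaires, will be blinded to treatment allocation", while "This study is an open-labeled trial and patients are not blinded". Asking patients about side effects at the visit that yields the primary outcome could reveal the regimen to whoever performs the test. This objection is sound, and the remedy has to deal with it.

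**Conclusion.** The mismatch is real and minor. If the plan is followed as written, new non-serious events starting on about days 16 to 44 have no systematic ascertainment, although the protocol counts them. The size is 29 calendar days, about half of the window from consent. This rests on a 30-day month and on the day-15 survey covering all earlier days. The clinical size is unknown.

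A reader might go further and conclude that the safety comparison is biased or that the adverse-event outcome is invalid. The documents do not support either. The schedule is the same in both arms and no differential reporting is shown. The primary analysis and sample size do not use these data.

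The severity discrepancy is clerical. Table 5 has no competing scale within the SAP, but its footnotes do not name the scale used.

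**What to change.** 1. In the Protocol Schedule, add an adverse-event and serious-event enquiry, with onset dates, at the existing day-56 visit. It should be asked by existing blinded questionnaire staff who neither perform nor read that patient's breath test, and before the result is known. Assign events to the Section 8 window by onset date.
2. In Protocol 9.2 and SAP 5.1, state that the adverse-event rate is the 14-day diary rate. List events from then to one month after treatment separately by arm, with the patients asked at day 56 as denominator.
3. In SAP 2.3, state that a missed day-56 enquiry does not count as missing safety data, so that a patient with day-15 data stays in the 14-day rate.
4. Reconcile 8.1 with 9.2, and name the SAP 5.1 scale under Table 5.

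The cost is a few questions at a visit where adverse-event treatment cost is already due, plus wording; no new visit is needed. It also needs no new staff if each site can separate the questionnaire from the breath test, which the documents do not settle. The drawbacks are about 41 days of recall by patients who know their treatment, and no late data on those who miss day 56, about 35 to 38 of 382 by the plan's own allowance.

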8.1 AE's degree

Mild: patients are easier to accept without induced questions, or patients have only mild discomfort which does not affect their daily lives and there is no need for clinical treatment.

Moderate: patients actively describe the symptoms that affect the life, but they can tolerate, which doesn't need clinical treatment.

Severe: patients have objective manifestations, which significantly affect the life, but patients can or can't bear, which needs clinical treatment.

8.2 Records and follow-up of AE

During the study, AE will be accurately recorded, including the time of occurrence, severity, duration, the measures taken and the outcome. Researchers will follow all the AE until the symptoms of patients disappeared or condition become stable. SAE should be tracked until a proper solution is found even though the study is over.

8.3 Serious adverse event (SAE)

(1)The judgments of SAE:

- Death, Life-threatening,
- Leading to hospitalization or prolong hospitalization time,
- Permanent or severe disability,
- Congenital Anomaly/Birth Defect.

(2)SAE report system:

Principal investigator and the hospital ethics committee should be reported and SAE report form should be filled in within 24 hours by phone no matter whether any kinds of SAE are related with the drug in 30 days after the treatment. And the form should be reported to national drug administration in time by principal investigator. SAE should be promptly handled, closely tracked until it is properly solved.

Contact method:

1) Contact persons: [name] [name]

2) SFDA Safety Supervision

9. Outcome Measures

9.1 Primary Outcome Measure:

1. Helicobacter pylori eradication rate

Six weeks after completion of therapy, H. pylori eradication success is defined as negative result from urea breath test (<4%). If patients would be lost to follow-up urea breath testing, they will be scored as treatment failures in the ITT analysis. The eradication rate is defined as the number of patients who successful eradicate *H. pylori* divided by the total number of population for analysis.

9.2 Secondary Outcome Measure

(1) Rate of adverse events

During the 14-day treatment period, the subjects will keep a diary to score any possible side effects or discomforts. The subjects will be asked to grade the severity of adverse events according to their influence on daily activities, experienced as “mild” (transient and well tolerated), “moderate” (causing discomfort and partially interfering with daily activities), or “severe” (causing considerable interference with daily activities). The side effect score recorded is based on the most severe event. Rate of adverse events is defined as the number of patients with any adverse event divided by the total number of population for analysis.

(2) Compliance rate

Compliance was defined as either poor when they had taken less than 80% of the total medication or good when they had taken more than 80% medication. Compliance rate is defined as the number of patients with good compliance divided by the total number of population for analysis.

9.3 Other Pre-specified Outcome Measures:

(1) Medical cost per patient of tailored or empiric therapy

Medical cost of one patient is overall cost including visit, endoscopy, H. pylori culture, susceptibility testing, eradication treatment, and adverse event treatment.

(2) Ratio of medical cost to H. pylori eradication rate of each therapy

(3) Ratio of incremental medical cost to incremental H. pylori eradication rate of tailored compared with empiric therapy

10. Statistical Methods

10.1 Sample size

Assuming 96.5% eradication rate of tailored therapy in our trial, 88.9% eradication rate of empirical therapy, a superiority margin of >0 , a power of 80%, an alpha of 0.05 (one-sided), a ratio of 3:1, at least 260 subjects in susceptibility-based therapy and 87 subjects in empirical therapy will be required to show superiority of susceptibility-based therapy over empirical therapy on the basis of H. pylori eradication rate. Taking into consideration of 10% lost to follow-up, at least 382 participants (286 for tailored therapy and 96 for empiric therapy) is expected to be recruited for the study.

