10.2 Statistical Analysis Data

Intention--to-treat (ITT) Analysis population: According to the Intention-to-treat principle: All randomized patients will be included in the ITT analysis. Patients who did not return for a follow-up 13C-UBT will be recorded as treatment failures.

Per-protocol (PP) analysis population: All individuals who violated the study protocol, such as patients not taking at least 80% of treatment drugs, or with unknown post-treatment H. pylori status will be excluded from the PP analysis.

Safety analysis population: The patients with missing safety data in ITT population will be excluded from the safety analysis.

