10.3 Statistical methods

Comparative superiority of the two groups was assessed through hypothesis testing (one-sided Z test) and derivation of a two-sided 95% confidence interval (CI) of difference based on H. pylori eradication rate. If p-value of the testing less than 0.025 and the lower bound of the 95% CI greater than zero, superiority of susceptibility-based therapy over empirical therapy could be concluded.

Between-group differences were evaluated using Student's t-test for continuous variables and Pearson's χ^2 /corrected χ^2 or Fisher's exact test for categorical variables, as appropriate. All p-values were two-sided except the testing of superiority, and were considered statistically significant if p-value less than 0.05.

Subgroup analyses of eradication efficacy were performed based on the results of antibiotic susceptibility test and compliance assessment.

11 Ethical principles

The study is registered in ClinicalTrials.gov. The study protocol is approved by the Ethics Committee at all institutions, and the study will be performed according to good clinical practice and the Declaration of Helsinki.

Before each patient is selected into the study, the physician of the study have the responsibility to tell patients or their designated agents the purpose, process, completion and comprehensively introduce possible adverse reactions, risks to bear, possible benefits and other information all-round and detailed, making the patients know their rights. We are ordered to inform the patients of having the right to decide whether to participate in the study, as well as the right to withdraw the study at any time without any discrimination. The patients or their legal representatives should sign the informed consent after carefully reading and fully understanding, and retain the signature page of the copy.

12 References

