Subjects without AEs

Subjects with AEs

Total

AE, adverse event.

Final Statistical Analysis Plan

This statistical analysis plan includes the details of study sample size calculation and statistical methods for analysis of outcomes and safety.

Table of Contents

1. Sample size estimation	68
2. Definition of populations for analysis	68
3. Evaluation of baseline characteristics	68
4. Evaluation of primary outcomes	70
5. Evaluation of secondary outcomes	70
6. Additional analyses	72
7. Table Design	73

1. Sample size estimation

Assuming 96.5% eradication rate of susceptibility-based therapy in our trial, 88.9% eradication rate of empirical therapy, a superiority margin of >0 , a power of 80%, an alpha of 0.05 (one-sided), a ratio of 3:1, at least 260 subjects in susceptibility-based therapy and 87 subjects in empirical therapy will be required to show superiority of susceptibility-based therapy over empirical therapy on the basis of H. pylori eradication rate. Taking into consideration of 10% lost to follow-up, at least 382 participants (286 for tailored therapy and 96 for empiric therapy) is expected to be recruited for the study.

2. Definition of populations for analysis

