4.3 Testing the superiority of the tailored therapy

Testing the superiority of tailored therapy group to empiric therapy group will be performed in the ITT and PP analysis populations using hypothesis testing (one-sided Z test) and derivation of a two-sided 95% confidence interval (CI) of difference based on *H. pylori* eradication rate. If p-value of the testing less than 0.025 and the lower bound of the 95% CI greater than zero, superiority of susceptibility-based therapy over empirical therapy could be concluded.

5. Evaluation of secondary outcomes

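### The sample size is computed at one-sided alpha 0.05, but superiority requires one-sided p below 0.025: the stated 80% power is about 72% at 260/87, or 76% if all 286/96 count

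*Combined protocol and SAP*

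**What the plan says.** **Sample size.** Final Protocol 10.1 sets the rates: "Assuming 96.5% eradication rate of tailored therapy in our trial, 88.9% eradication rate of empirical therapy". It then states "a power of 80%, an alpha of 0.05 (one-sided), a ratio of 3:1, at least 260 subjects in susceptibility-based therapy and 87 subjects" in the empirical arm, and adds an allowance for loss: "Taking into consideration of 10% lost to follow-up, at least 382 participants (286 for tailored therapy and 96 for empiric therapy"). Final SAP section 1 repeats the calculation with the same level: "a power of 80%, an alpha of 0.05 (one-sided), a ratio of 3:1".

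**Decision rule.** Final Protocol 10.3 compares the arms with a one-sided Z test and a two-sided 95% confidence interval for the difference. Superiority may be concluded on this condition: "If p-value of the testing less than 0.025 and the lower bound of the 95% CI greater than zero". Final SAP 4.3 uses the same condition, with the analysis "performed in the ITT and PP analysis populations using hypothesis testing (one-sided Z test) and derivation of a two-sided 95% confidence interval".

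**Missing outcomes.** Final Protocol 10.2 says of the intention-to-treat analysis: "Patients who did not return for a follow-up 13C-UBT will be recorded as treatment failures".

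The plan does not say whether the assumed rates apply to evaluable patients or to everyone randomized. It also does not name the confidence interval method or say whether the Z test uses a pooled variance.

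**The concern.** Power has meaning only for a specific decision rule. The number of patients was derived for a test at one-sided 0.05, while the conclusion will be drawn at one-sided 0.025 with a matching 95% interval. The stricter rule is harder to satisfy with the same patients, so the true power must be below 80%, and nothing in the plan makes up the difference.

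Showing superiority is the primary objective, and 80% is the plan's own statement of its chance of doing so. A null result would be read against a 20% risk of missing the assumed effect, when under the plan's rule that risk is about 24% to 28%. The mismatch runs in the conservative direction for false positives and does not affect the estimated difference.

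**Working it through.** **Inputs (Final Protocol 10.1 and 10.3).** Tailored p_T = 0.965; empirical p_E = 0.889; difference d = 0.076; ratio k = 3; power 0.80 (z = 0.8416); sizing level one-sided 0.05 (z = 1.6449); decision level one-sided 0.025 (z = 1.9600).

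**1. Reproduce the plan's figure.** Pooled two-proportion formula for the empirical arm:

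n_E = [z_alpha × √(p̄(1−p̄)(1+1/k)) + z_beta × √(p_E(1−p_E) + p_T(1−p_T)/k)]² / d²

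- p̄ = (0.889 + 3 × 0.965)/4 = 0.946
- First root: √(0.051084 × 4/3) = 0.26098
- Second root: √(0.098679 + 0.033775/3) = 0.33157
- One-sided 0.05: (1.6449 × 0.26098 + 0.8416 × 0.33157)² / 0.076² = (0.42928 + 0.27905)² / 0.005776 = 86.9, and 3 × 86.87 = 260.6

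This matches the stated 260/87. Other formulas at 0.05 fit less well (empirical arm 104 with continuity correction, 118 unpooled, about 90 by arcsine).

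**2. Same formula at the decision level.** (1.9600 × 0.26098 + 0.27905)² / 0.005776 = (0.51152 + 0.27905)² / 0.005776 = 108.2, so 109 empirical and 327 tailored. The 0.05 in section 10.1 is therefore the level actually used, not a misprint for 0.025.

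**3. Power at the planned numbers.** Power = Φ[(d − z_alpha × s0)/s1], where s0 is the pooled and s1 the unpooled standard error of the difference.

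- 260/87 at 0.05: (0.076 − 1.6449 × 0.028007)/0.035555 = 0.842, power 80.0%
- 260/87 at 0.025: (0.076 − 1.9600 × 0.028007)/0.035555 = 0.594, power 72.4%
- 286/96 at 0.025: (0.076 − 1.9600 × 0.026683)/0.033853 = 0.700, power 75.8%

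**4. Exact binomial power at one-sided 0.025, alone and with the interval condition.**

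| Rule | 260/87 | 286/96 |
|---|---|---|
| Pooled Z test alone | 72.9% | 76.4% |
| and Miettinen-Nurminen lower bound above zero | 72.9% | 75.6% |
| and Newcombe lower bound above zero | 71.6% | 75.6% |
| and Wald lower bound above zero | 59.3% | 65.0% |

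A score or Newcombe interval costs at most about one point; a Wald interval costs much more. The pooled Z test is inferred from step 1; an unpooled Z test would give the Wald row.

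**5. Side calculation, separate from the alpha error.** Section 10.1 inflates by multiplication (260 × 1.10 = 286; 87 × 1.10 = 95.7, rounded to 96), which suggests evaluable-patient rates. If so, and if loss is equal in both arms (an assumption), scoring missing breath tests as failures multiplies both rates by (1 − loss). Exact pooled-Z power at 286/96 and one-sided 0.025 is then:

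- 5% loss (91.7% v 84.5%): about 52%, or 42% if a Wald interval is also required
- 10% loss (86.9% v 80.0%): about 38%, or 30% if a Wald interval is also required

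**The case against.** The best textual defence is the closing sentence on p-values in section 10.3, which sets a general significance threshold of 0.05. It does not help. The superiority test has its own threshold of 0.025, and even at a p-value threshold of 0.05 the requirement that a two-sided 95% interval exclude zero would still impose a one-sided 2.5% level.

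A second argument is that this is only a planning statement. The decision rule is clear, is the same in protocol and SAP, and is the stricter of the two levels; a reported interval will show the reader how precise the result is. All of that is true, and it limits the harm to the stated power. It does not make the 80% correct.

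Three cautions about the correction have some force:

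- Changing the alpha alone would misdescribe how 260/87 was obtained, so alpha and power must change together.
- The 72% is power among evaluable patients and must be labelled so. Under that reading, intention-to-treat power is lower (step 5).
- The Wald figures depend on a method the plan has not chosen, so they are conditional and not part of the main finding.

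**Conclusion.** The stated power is wrong as written. Under the plan's own rule and assumed rates it is about 72% at 260/87 if the rates are evaluable-patient rates, or about 76% at 286/96 if they are intention-to-treat rates with everyone counted. The shortfall from 80% is about 4 to 8 points, and power is below 80% under either reading.

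These figures assume a pooled Z test, which is the favourable case; exact calculation moves them by about half a point. If the interval condition is applied with a Wald interval, exact power is about 59% or 65%. The effect of missing breath tests is a further issue that depends on what the assumed rates represent. Neither is needed for the main conclusion, which rests on the two alpha levels in the text.

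**What to change.** In Final Protocol 10.1 and Final SAP section 1, in one edit:

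- Give the level as one-sided 0.025, to match Protocol 10.3 and SAP 4.3, and remove the claim that 260/87 yields 80% power.
- Say whether 96.5% and 88.9% are evaluable-patient or intention-to-treat rates.
- Restate power as about 72% at 260/87 evaluable patients (evaluable rates), or about 76% at 286/96 randomized (intention-to-treat rates).
- Note that power is lower, about 59% or 65% respectively, if a Wald interval is used for the interval condition. Naming the test and interval would settle which figure applies.

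The cost is two wording changes and a less favourable power figure. No extra enrolment is asked for. For information, 80% power at one-sided 0.025 would need about 327/109 evaluable patients (436). With 10% loss that is 364/122 recruited (486) dividing by 0.9, or 360/120 (480) by the plan's own multiplication by 1.10.

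Relaxing the decision rule to one-sided 0.05 is not proposed. It would loosen the false-positive criterion and conflict with the 95% interval requirement.
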